### 3.3.2. Intervention

Patients who meet the eligibility criteria and are randomized to one of the treatment arms, will receive either topotecan alone intravenously at 1.25 mg/m^2 on days 1 to 5 of a 21-day cycle or pembrolizumab alone administered intravenously at 200mg every 21 days.

During the study period, patients will be evaluated clinically by physical exam and with routine blood work every 21 days. Adverse events will be monitored throughout the study and graded in severity according to the guidelines outlined in the NCI Common Terminology Criteria for Adverse Events (CTCAE) version 4. Pre-specified adverse events of clinical interest include: 1) Grade  $\geq$  2 diarrhea, 2) Grade  $\geq$  2 colitis, 3) Grade  $\geq$  2 pneumonitis, 4) Grade  $\geq$  2 hepatitis 5) Grade  $\geq$  3 hypo- or hyperthyroidism.

Patients will be evaluated every 6 weeks ( $42 \pm 7$  days) with radiographic imaging to assess response to treatment. Investigators will make all treatment-based decisions using RECIST 1.1. Patients will continue to receive topotecan or pembrolizumab every three weeks until documented disease progression, unacceptable side effects, intercurrent illness that prevents further administration of treatment, investigator's decision to withdraw the patient, patient withdraws consent, pregnancy of the patient, non-compliance with study treatment or procedure requirements or administrative reasons. Patients on the topotecan arm who progress on study will be allowed to cross-over to the pembrolizumab arm.

After the end of treatment, each patient will be followed for a minimum of 30 days for adverse event monitoring. Serious adverse events will be collected for up to 90 days after the end of treatment or 30 days after the end of treatment if the subject initiates new anticancer therapy, whichever is earlier. Immune related serious adverse events will be followed for 90 days after end of treatment. Subjects who discontinue treatment for reasons other than disease progression will have posttreatment follow-up every 6 weeks for disease status until progression, initiating a non-study cancer treatment, withdrawing consent, or becoming lost to follow-up. All subjects will be followed by telephone contact every 3 months for overall survival until death or withdrawal of consent.

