## 9. SCHEDULE OF ASSESSMENTS

### 9.1. SCHEDULE OF ASSESSMENTS

**Table 2. Schedule of Assessments**

Study Period:	Treatment Cycles 								End of Treatment §	Post-Treatment Evaluations			
	Treatment Cycle/Title:	Screening (Visit 0)	1	2	3	4	To be repeated beyond 8 cycles			At time of treatment discontinuation	Safety Follow-up 	Follow Up Visits 	Survival Follow-Up 
5							6	7	8				
Scheduling Window (Days)  :	-14 to -1		± 3	± 3	± 3	± 3	± 3	± 3	± 3	At time of treatment discontinuation	30 days	Every 6 weeks	Every 12 weeks
Informed Consent 	X												
Inclusion/Exclusion Criteria 	X												
Demographics	X												
Medical History 	X	X	X	X	X	X	X	X	X	X	X	X	X
Prior and Concomitant Medication Review 	X	X	X	X	X	X	X	X	X	X			
SCLC Disease Details 	X												
Study Treatment Administration		X	X	X	X	X	X	X	X				
Review Adverse Events 		X	X	X	X	X	X	X	X	X	X	X	X
Physical Examination	X	X	X	X	X	X	X	X	X		X	X	
Vital Signs and Weight 	X	X	X	X	X	X	X	X	X	X	X	X	X
ECOG Performance Status	X	X	X	X	X	X	X	X	X	X	X	X	X
Pregnancy Test – Urine or Serum β-HCG 	X	X											
PT/INR and aPTT 	X												
CBC with Differential 	X		X	X	X	X	X	X	X	X	X		
Comprehensive Serum Chemistry Panel 	X		X	X	X	X	X	X	X	X	X		
Urinalysis 	X				X				X	X			

Study Period:	Treatment Cycles 									End of Treatment §	Post-Treatment Evaluations		
Treatment Cycle/Title:	Screening (Visit 0)	1	2	3	4	To be repeated beyond 8 cycles				At time of treatment discontinuation	Safety Follow-up 	Follow Up Visits 	Survival Follow-Up 
						5	6	7	8				
Scheduling Window (Days)  :	-14 to -1		± 3	± 3	± 3	± 3	± 3	± 3	± 3	At time of treatment discontinuation	30 days	Every 6 weeks	Every 12 weeks
T3, FT4 and TSH 	X		X		X		X		X	X			
EKG	X												
Tumor Imaging (CT Scan/MRI) 	X		X		X		X		X	X		X	
Archival or Newly Obtained Tissue Collection 	X												
Newly Obtained Tissue Collection	X 		X 							X 			
Correlative Studies Blood Collection 	X		X		X		X		X				

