-  In general, assessments/procedures are to be performed on day 1 and prior to the first dose of study treatment for each cycle unless otherwise specified. Treatment cycles are 3 weeks (21-days); however the treatment cycle interval may be increased due to toxicity according to the dose modification guidelines provided in Section 13. If treatment cycles are increased all procedures except imaging will be completed according to cycle number and not weeks on treatment, imaging will be performed every 6 weeks ( $\pm 7$  days) from the first dose of study treatment regardless of any treatment delays during the first 8 cycles.
-  In general, the window for each visit is  $\pm 3$  days unless otherwise specified.
-  Written consent must be obtained prior to performing any protocol specific procedure. Results of a test performed prior to the patient signing consent as part of routine clinical management are acceptable in lieu of a screening test if performed within the specified time frame. Informed consent and assessment of eligibility criteria can be obtained 21 days prior to the start of treatment.
-  Medical history should be completed by study staff and include all comorbidities, as well as a detailed assessment of smoking history: number of years of tobacco smoke, packs of cigarettes smoked, ongoing tobacco smoke or time since quitting smoking. This will also include documentation of SCLC disease status.
-  Prior medications – record all medications taken within 14 days of visit 1 and all treatments for a prior cancer other than SCLC. After the Safety Follow-up Visit record all medications taken for SAEs and ECIs as defined in Section 17.
-  Disease details are to be collected, including: sites of disease; first-line chemotherapy (cisplatin vs carboplatin); number of cycles of first-line chemotherapy; administration of prophylactic cranial irradiation, consolidative mediastinal radiation or palliative radiation to an osseous site; best response to prior therapy (stable disease, partial response, complete response, progression of disease); time to relapse (sensitive disease vs resistant disease).
-  AEs and laboratory safety measurements will be graded per NCI CTCAE version 4.0. All AEs, whether gradable by CTCAE or not will also be evaluated for seriousness.

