-  Baseline tumor imaging will include the following: CT chest and abdomen with contrast OR CT chest without contrast and MRI abdomen with/without gadolinium and imaging of other known sites of disease; and brain imaging with MRI with/without contrast (or CT with contrast if the patient cannot tolerate an MRI). Imaging of the pelvis should be performed as clinically indicated or if there is known metastases in the pelvis. The initial tumor imaging will be performed within 14 days prior to the first dose of study treatment. Scans performed as part of routine clinical management are acceptable for use as the screening scan if they are of diagnostic quality and performed within 14 days prior to the first dose of study treatment. On-study imaging will be performed every 6 weeks ( $42 \pm 7$  days) after the first dose of study treatment or more frequently if clinically indicated. **The timing for imaging studies should follow calendar days and should not be adjusted for delays in cycle starts or extension of topotecan or pembrolizumab cycle frequencies.** The same imaging technique should be used in a patient throughout the study. Local reading (investigator assessment with site radiology reading) will be used to determine eligibility and for patient management.
-  After first documentation of progression (if the patient is clinically stable) or response per RECIST 1.1 repeat imaging for confirmation is required. Confirmatory imaging may be performed as early as 28 days later; alternatively, the scan performed at the next scheduled time point may be used as confirmation.
-  Tumor tissue for biomarker analysis from an archival tissue sample (not more than 42 days prior to signing consent) or newly obtained tumor tissue from a recent biopsy of a tumor lesion not previously radiated. Please see AFT 17 Correlative Science Manual for specimen collection instructions. If a NEW biopsy is performed, the investigator should ensure that adequate tissue is collected.

-  Patients who discontinue study treatment for a disease progression, will undergo a mandatory Safety Follow-up Visit approximately 30 days after the last dose of study treatment or before the initiation of a new antineoplastic treatment, whichever comes first. Patients with an AE of grade > 1 will be further followed until the resolution of the AE to Grade 0-1 or until beginning of a new antineoplastic therapy, whichever occurs first.

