-  Patients who discontinue study treatment for a reason other than disease progression will move into the Follow-up Phase and should be assessed every 6 weeks ( $42 \pm 7$  days) by radiologic imaging to monitor disease status, development of drug related SAEs and ECIs/irAEs, and initiation of a new antineoplastic therapy. Follow-up visit 1 should be scheduled 6 weeks after the last dose of study treatment. Unless otherwise noted in the flow chart, every effort should be made to collect patient information until the start of new antineoplastic therapy, disease progression, or death, whichever comes first.
-  Once a patient experiences disease progression or starts a new antineoplastic therapy, the patient moves into the Survival Follow-up Phase and should be contacted by telephone every 3 months to assess for survival status, development of drug related SAEs and ECIs/irAEs and the start of new antineoplastic therapy if applicable.
-  Record all AEs occurring within 30 days after the last dose of study treatment or until initiation of a new antineoplastic therapy, whichever comes first. Report all SAEs (related and unrelated to study treatment) occurring within 90 days of the last dose of study treatment or the start of new anti-cancer treatment, whichever comes first. All ECIs/irAEs occurring within 90 days of the last dose of study treatment should be reported regardless of initiating new anticancer therapy. After this time, report only SAEs and ECIs/irAEs that are considered related to study treatment.
-  If archival sample is not available, fresh tissue samples will be collected for correlative studies.
-  Those patients receiving pembrolizumab will undergo a biopsy obtained during week 4 to 6 of treatment for biomarker analysis, if clinically feasible and safe. A tumor lesion not previously radiated (required for PD-L1 determination) should be biopsied. The tumor sample must be sent to the AFT-Biorepository. See AFT 1 Correlative Science Manual for additional details.
-  Patients on the topotecan arm who progress and are to cross-over to the pembrolizumab arm, will undergo a biopsy just before initiating experimental treatment, if clinically feasible and safe. A tumor lesion not previously radiated (required for PD-L1 determination) should be biopsied. The tumor sample must be sent to the AFT-Biorepository.

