Renal Failure or Nephritis	2	Toxicity resolves to Grade 0-1	Toxicity does not resolve within 6 weeks of last dose or inability to reduce corticosteroid to 10 mg or less of prednisone or equivalent per day within 6 weeks
	3-4	Permanently discontinue	Permanently discontinue
All Other Drug-Related Toxicity, excluding hematologic toxicity	3 or Severe	Toxicity resolves to Grade 0-1	Toxicity does not resolve within 6 weeks of last dose or inability to reduce corticosteroid to 10 mg or less of prednisone or equivalent per day within 6 weeks
	4	Permanently discontinue	Permanently discontinue
Hematologic Toxicity			
Thrombocytopenia associated with bleeding	3	Toxicity resolves to Grade 0-1 or baseline May increase the dosing interval by 1 week	Toxicity does not resolve within 6 weeks of last dose Permanently discontinue if associated with severe or life threatening bleeding event
Neutropenia, anemia, or thrombocytopenia	4	Toxicity resolves to Grade 0-1 or baseline May increase the dosing interval by 1 week	Toxicity does not resolve within 6 weeks of last dose Permanently discontinue if associated with any severe or life threatening event
Note: Permanently discontinue for any severe or Grade 3 drug-related AE that recurs or any life-threatening event.			
 For patients with liver metastasis who begin treatment with Grade 2 AST or ALT, if AST or ALT increases by greater than or equal to 50% relative to baseline and lasts for at least 1 week then patients should be discontinued.			
 If symptoms resolve within one hour of stopping drug infusion, the infusion may be restarted at 50% of the original infusion rate (e.g., from 100 mL/hr to 50 mL/hr). Otherwise dosing will be held until symptoms resolve and the subject should be premedicated for the next scheduled dose: Refer to Table 8 Infusion Treatment Guidelines for further management details.			
 Patients with intolerable or persistent Grade 2 drug-related AE may hold study medication at physician discretion. Permanently discontinue study drug for persistent Grade 2 adverse reactions for which treatment with study drug has been held, that do not recover to Grade 0-1 within 6 weeks of the last dose.			

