The End of Treatment and Follow-up visit procedures are listed in Section 9. After the end of treatment, each patient will be followed for a minimum of 30 days for adverse event monitoring. Serious adverse events will be collected for up to 90 days after the end of treatment or 30 days after the end of treatment if the subject initiates new anticancer therapy, whichever is earlier. Patients who discontinue for reasons other than progressive disease will have post-treatment follow-up for disease status every 6 weeks until disease progression, initiating a non-study cancer treatment, withdrawing consent or becoming lost to follow-up. After documented disease progression each patient will be followed by telephone every 12 weeks for overall survival until death, withdrawal of consent, or the end of the study, whichever occurs first.

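### The day-30 safety visit is required only after a stop for progression, so patients who stop for toxicity have no scheduled blood count or chemistry after End of Treatment

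*Combined protocol and SAP*

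**What the plan says.** Section 9.1 splits patients who stop treatment into two groups by reason.

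- **Progression (footnote 19, attached to the Safety Follow-up column of Table 2):** "Patients who discontinue study treatment for a disease progression, will undergo a mandatory Safety Follow-up Visit", timed at about 30 days after the last dose, or earlier if a new cancer treatment is about to start.
- **Any other reason (footnote 20):** the patient enters the Follow-up Phase with 6-weekly assessment (42 ± 7 days). "Follow-up visit 1 should be scheduled 6 weeks after the last dose of study treatment". The footnote does not mention a day-30 visit.

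In Table 2, the row "CBC with Differential" and the serum chemistry row are marked at End of Treatment and Safety Follow-up. Both are blank under Follow Up Visits and Survival Follow-Up.

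Other text covers every patient. Section 3.3.2 states: "After the end of treatment, each patient will be followed for a minimum of 30 days for adverse event monitoring". Section 16.2.1 repeats that "each patient will be followed for a minimum of 30 days for adverse event monitoring". Footnote 22 says "Record all AEs occurring within 30 days after the last dose of study treatment", ending sooner if new therapy begins. Footnote 5 says "After the Safety Follow-up Visit record all medications taken for SAEs and ECIs as defined in Section 17", with no limit on who has that visit.

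**The concern.** This is a patient-safety point. The schedule gives less laboratory monitoring to the group more likely to need it. Table 5 requires immediate permanent stops of pembrolizumab for events followed by blood tests, such as grade 3–4 liver test elevation (with a stated exception) and grade 3–4 renal failure or nephritis. Its general note adds: "Permanently discontinue for any severe or Grade 3 drug-related AE that recurs or any life-threatening event". Table 7 takes topotecan patients off study for neutropenic fever or a creatinine clearance below 20 ml/min. After End of Treatment none of these patients has a scheduled blood count or chemistry panel, whereas a patient who stops for progression has one.

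The protocol's own reporting duties depend on such tests. Section 17.2.2 defines one event of clinical interest entirely by AST or ALT, bilirubin and alkaline phosphatase values, and footnote 22 requires these events to be reported for 90 days. After a non-progression stop, only an unscheduled test could reveal one once End of Treatment has passed.

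No bias in the comparison of adverse events between arms is claimed, and neither the PFS analysis nor the sample size is affected.

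**Working it through.** The plan states no figure to reproduce. The check is a reading of Table 2 with its footnotes, followed by day counts.

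**Step 1. Post-treatment columns of Table 2.** Each row checked has 13 cells for 13 columns (Screening, cycles 1–8 and four post-treatment columns), so each mark can be placed without doubt.

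| Row | End of Treatment | Safety Follow-up (30 days) | Follow Up Visits (6-weekly) | Survival Follow-Up (12-weekly) |
|---|---|---|---|---|
| Blood count | X | X | – | – |
| Chemistry | X | X | – | – |
| Thyroid tests, urinalysis | X | – | – | – |
| Adverse event review, vital signs | X | X | X | X |
| Physical examination | – | X | X | – |
| Imaging | X | – | X | – |

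**Step 2. Scheduled blood count and chemistry sets after End of Treatment.**

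- Stop for progression: Safety Follow-up = 1.
- Stop for any other reason: none marked at Follow Up Visits or Survival Follow-Up = 0.

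**Step 3. First scheduled visit after End of Treatment for other stops.** Footnote 20 gives 42 ± 7 days from the last dose.

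- Earliest: 42 − 7 = day 35, which is 35 − 30 = 5 days after day 30.
- Latest: 42 + 7 = day 49, which is 49 − 30 = 19 days after day 30.

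Physical examination is not marked at End of Treatment, so this visit is also the next scheduled examination after the last cycle visit.

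**Step 4. When the End of Treatment bloods fall.** The protocol does not say when in a cycle a stop is decided. I assume the next pembrolizumab Day 1, 21 ± 3 days after the last dose.

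- End of Treatment bloods: 21 − 3 = day 18 to 21 + 3 = day 24.
- Distance to day 30: 30 − 24 = 6 to 30 − 18 = 12 days.

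A stop decided earlier in the cycle would lengthen this interval.

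**Step 5. Where there is no gap.** Table 5 also allows pembrolizumab to be stopped when a toxicity has not resolved within 6 weeks of the last dose. End of Treatment bloods then fall at about 6 × 7 = day 42, already past day 30. Section 14.1.2 similarly withdraws topotecan patients once 6 weeks have passed since the last cycle began. If all five daily doses were given, that is 42 − 4 = 38 days after the last dose, also past day 30.

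**The case against.** The strongest reply is that footnote 19 names one group without excluding the other. The Safety Follow-up column is headed 30 days with no restriction by reason, footnote 5 assumes the visit generally, sections 3.3.2 and 16.2.1 promise 30 days of monitoring to each patient, and footnote 20 does not say that its visits replace the day-30 visit. On this view the footnote is a drafting slip. That may well be so, but nothing schedules the visit for other stops, and a site following the two footnotes literally would not hold it.

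A second reply is that patients stopped for severe toxicity are the best covered by other rules. Footnote 19 follows events above grade 1 to grade 0–1 or new therapy, serious events are followed to outcome, and following a hepatic, renal or haematologic event in practice requires blood tests. This stands, and it narrows the gap to a new laboratory abnormality without symptoms between End of Treatment and day 30. It does not close the gap, because following a known event does not schedule a test for an unknown one.

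Three smaller points also stand. The 6 to 12 days depend on an assumed stop date. The visit after a progression stop can itself come early if new therapy starts. No footnote will produce bloods from a patient who withdraws consent or is lost to follow-up.

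**Conclusion.** The concern holds. As written, the schedule provides one blood count and chemistry set after End of Treatment for patients who stop for progression and none for those who stop for any other reason. The latter have no scheduled visit until day 35 to 49. The count and these days come directly from Table 2 and footnotes 19 and 20. Only the 6 to 12 days between End of Treatment bloods and day 30 rest on an assumption, namely that the stop is decided at the next pembrolizumab Day 1.

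The gap is confined to scheduled visits and laboratory tests, and mainly to immediate permanent stops. The documents do not allow the number of patients affected to be estimated. The change is still worth making: the literal rule gives patients stopped for toxicity less scheduled monitoring than those stopped for progression, and it sits badly with the 30-day monitoring promised to everyone.

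**What to change.** In footnote 19, replace the restriction to progression with discontinuation for any reason. Keep the existing timing of about 30 days after the last dose, or before new cancer treatment if that comes first. In footnote 20, state that the 6-weekly Follow-up Phase is in addition to the Safety Follow-up Visit.

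The cost is wording in two footnotes and one extra routine visit with bloods for each affected patient. The visit and its tests are already in Table 2, so no new procedure is needed.

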**Table 3. Laboratory Tests**

Hematology	Chemistry	Urinalysis	Other
Hematocrit	Albumin	Blood	Serum pregnancy test ( $\beta$ -human chorionic gonadotropin, $\beta$ -hCG )†
Hemoglobin	Alkaline phosphatase	Glucose	PT (INR)
Platelet count	Alanine aminotransferase (ALT)	Protein	aPTT
WBC (total and differential, including absolute neutrophil count)	Aspartate aminotransferase (AST)	Specific gravity	Total thriiodothyronine (T3)
Red Blood Cell Count		Microscopic exam ( If abnormal )	Free tyroxine (T4)
	Carbon Dioxide ‡ (CO 2 or bicarbonate)	results are noted	Thyroid stimulating hormone (TSH)
	Calcium		
	Chloride		
	Glucose		
	Potassium		
	Sodium		
	Total Bilirubin		
	Direct Bilirubin ( If total bilirubin is elevated above the upper limit of normal )		
	Total protein		
	Blood Urea Nitrogen		

† Perform on women of childbearing potential only. If urine pregnancy results cannot be confirmed as negative, a serum pregnancy test will be required.

‡ If considered standard of care in your institution.

Laboratory tests for screening should be performed within 14 days prior to the first dose of treatment. After Cycle 1, pre-dose laboratory procedures can be conducted up to 72 hours prior to dosing. Results must be reviewed by the investigator or qualified designee and found to be acceptable prior to each dose of study treatment. At cross-over, laboratory tests can be performed up to 72 hours prior to dosing of pembrolizumab.

## **9.2. TUMOR IMAGING SCHEDULE**

The initial tumor imaging will be performed within 14 days prior to the first dose of study treatment. Scans performed as part of routine clinical management are acceptable for use as the screening scan if they are of diagnostic quality and performed within 14 days prior to the first dose of study treatment.

On-study imaging will be performed every 6 weeks ( $42 \pm 7$  days) after the first dose of study treatment, or more frequently if clinically indicated. The timing for imaging studies should follow calendar days and should not be adjusted for delays in cycle starts or extension of pembrolizumab (MK-3475) or topotecan cycle frequencies. The same imaging technique should be used in a patient throughout the study. Local reading (investigator assessment with site radiology reading) will be used to determine eligibility and for patient management.

